#### Study Schedule for the extension period only, Protocol I3Y-MC-JPBK]

Patients experiencing ongoing clinical benefit may continue to receive abemaciclib or erlotinib in the extension period. There is no cross-over between the 2 study treatment arms.

Perform procedure as indicated.

			Patients on Study Treatment	Extension Period Follow-Up
		Cycle	2 – n	Follow-Up a
		Visit	501-5XX	901
		Duration (days)	28	30
		Relative day within a cycle	1	
Procedure Category	Procedure	Protocol Reference		
Adverse Event Grading b	ts Collection/CTCAE	Section 10.3.1	Х	Х
Study Drug	Abemaciclib or Erlotinib c	Section 9.1	Х	

Abbreviations: CTCAE = Common Terminology Criteria for Adverse Events; PK = pharmacokinetics; SAEs = serious adverse events.

- a The extension period begins after study completion and ends at the end of trial.
- b Data on SAEs that occur before the end of trial will be stored in the collection database and the Lilly safety system.
- Abemaciclib is to be administered every 12 hours (± approximately 2 hours) on Days 1 through 28 of each cycle. Erlotinib is to be administered every 24 hours (± approximately 2 hours) on Days 1 through 28 of each cycle.
   Note: Efficiency assessments will be done at the investigator's discretion based on the standard of care

Note: Efficacy assessments will be done at the investigator's discretion based on the standard of care.

# **Attachment 2. Protocol JPBK Clinical Laboratory Tests**

#### Clinical Laboratory Tests

Hematology a	Clinical Chemistry a
Hemoglobin	Serum Concentrations of:
Hematocrit	Sodium
Erythrocyte count (RBC)	Potassium
Mean cell volume (MCV)	Chloride
Mean cell hemoglobin concentration (MCHC)	Total bilirubin
Leukocytes (WBC)	Direct bilirubin
Neutrophils	Alkaline phosphatase
Lymphocytes	Alanine aminotransferase (ALT)
Monocytes	Aspartate aminotransferase (AST)
Eosinophils	Blood urea nitrogen (BUN)
Basophils	Creatinine
Platelets	Calcium
	Albumin
	Total Protein
	Pregnancy Test (females only)b

Serum

Abbreviations: RBC = red blood cells; WBC = white blood cells.

a Assayed by Lilly-designated laboratory.

b Local or investigator-designated laboratory.

#### **Other Laboratory Tests**

KRASa

Sanger Sequencingb

a Assayed by Lilly-designated central laboratory or with sponsor approval by local or investigator-designated laboratory.

b To be performed on the same samples used for *KRAS* central laboratory testing.

# Attachment 3. Protocol JPBK Hepatic Monitoring Tests for Treatment-Emergent Abnormality

Selected tests may be obtained in the event of a treatment-emergent hepatic abnormality and may be required in follow up with patients in consultation with the Lilly clinical research physician.

Hepatic Monitoring Tests	
Hepatic Hematology a	Haptoglobin a
Hemoglobin	
Hematocrit	Hepatic Coagulation a
RBC	Prothrombin Time
WBC	Prothrombin Time, INR
Neutrophils, segmented	
Lymphocytes	Hepatic Serologies a,b
Monocytes	Hepatitis A antibody, total
Eosinophils	Hepatitis A antibody, IgM
Basophils	Hepatitis B surface antigen
Platelets	Hepatitis B surface antibody
	Hepatitis B Core antibody
Hepatic Chemistry a	Hepatitis C antibody
Total bilirubin	Hepatitis E antibody, IgG
Direct bilirubin	Hepatitis E antibody, IgM
Alkaline phosphatase	
ALT	Anti-nuclear antibody a
AST	
GGT	Anti-smooth muscle antibody a
СРК	
Abbreviations: $AIT = algnine aminor$	transferase: AST = aspartate aminotransferase: CPK = creatine phosphok

Abbreviations: ALT = alanine aminotransferase; AST = aspartate aminotransferase; CPK = creatine phosphokinase; GGT = gamma glutamyl transferase; Ig = immunoglobulin; INR = international normalized ratio; RBC = red blood cells; WBC = white blood cells.

a Assayed by Lilly-designated laboratory.

b Reflex/confirmation dependent on regulatory requirements and/or testing availability.

# Attachment 4. Protocol JPBK ECOG Performance Status

Activity Status	Description
0	Fully active, able to carry on all pre-disease performance without restriction
1	Restricted in physically strenuous activity but ambulatory and able to carry out work of a light or sedentary nature, e.g., light house work, office work
2	Ambulatory and capable of all selfcare but unable to carry out any work activities. Up and about more than 50% of waking hours
3	Capable of only limited selfcare, confined to bed or chain more than 50% of waking hours
4	Completely disabled. Cannot carry on any selfcare. Totally confined to bed or chair
5	Dead.

Source: Oken et al. 1982.

# Attachment 5. Protocol JPBK RECIST Criteria 1.1

Response and progression will be evaluated in this study using the international criteria proposed by the New Response Evaluation Criteria in Solid Tumors (RECIST): Revised RECIST Guideline (version 1.1; Eisenhauer et al. 2009).

#### Measurability of Tumor at Baseline

Tumor lesions/lymph nodes will be categorized at baseline as measurable or nonmeasurable. Measurable disease is defined by the presence of at least 1 measurable lesion.

#### Measurable

Tumor lesions: Measured in at least 1 dimension (longest diameter in the plane of measurement is to be recorded) with a minimum size of:

- 10 mm by computed tomography (CT) or magnetic resonance imaging (MRI) scan (slice thickness ≤5 mm)
- 10 mm caliper measurement by clinical exam (non-measurable lesions if cannot be accurately measured with calipers)
- 20 mm by chest X-ray.

Malignant lymph nodes: To be considered pathologically enlarged and measurable, a lymph node must be  $\geq 15$  mm in short axis when assessed by CT scan (CT scan thickness recommended to be  $\leq 5$  mm).

#### Nonmeasurable

All other lesions, including small lesions (longest diameter <10 mm or pathological lymph nodes with  $\geq$ 10 to <15 mm short axis) as well as truly nonmeasurable lesions. Lesions considered truly non-measurable include: leptomeningeal disease, ascites, pleural/pericardial effusions, lymphangitis cutis/pulmonis, inflammatory breast disease, lymphangitis involvement of skin or lung, abdominal masses/abdominal organomegaly identified by physical exam that is not measureable by reproducible imaging techniques.

#### Special Considerations for Lesion Measurability

#### Bone lesions:

- Bone scan, PET scan or plain films are not considered adequate imaging techniques to measure bone lesions.
- Lytic bone lesions or mixed lytic-blastic lesions, with identifiable soft tissue components, that can be evaluated by cross sectional imaging techniques such as CT or MRI, can be considered measurable lesions if the soft tissue component meets the definition of measurability.
- Blastic bone lesions are non-measurable.

## Cystic lesions:

- Simple cysts should not be considered as malignant lesions (neither measurable nor nonmeasurable)
- Cystic lesions thought to represent cystic metastases can be considered as measurable lesions, if they meet the definition of measurability. If noncystic lesions are presented in the same patients, these are preferred for selection as target lesions.

## Lesions with Prior Local Treatment:

• Tumor lesions situated at a previously irradiated area, or in an area subjected to other loco-regional therapy, are non-measurable unless there has been demonstrated progression in the lesion.

## **Baseline Documentation of Target and Non-Target Lesion**

## Target Lesions

When more than 1 measurable lesion is present at baseline, all lesions up to a maximum of 5 lesions total (and a maximum of 2 lesions per organ) representative of all involved organs should be identified as target lesions and will be recorded and measured at baseline. Non-nodal Target lesions should be selected on the basis of their size (lesions with the longest diameter), be representative of all involved organs, and can be reproduced in repeated measurements.. Measurable lymph nodes are target lesions if they meet the criteria of a short axis of  $\geq 15$  mm by CT scan. All measurements are to be recorded in the case record form (CRF) in millimeters (or decimal fractions of centimeters [cm]).

## Nontarget Lesions

All other lesions (or sites of disease) are identified as nontarget lesions (chosen based on their representativeness of involved organs and the ability to be reproduced in repeated measurements) and should be recorded at baseline. Measurement of these lesions are not required but should be followed as 'present,' 'absent,' or in rare cases 'unequivocal progression.' In addition, it is possible to record multiple nontarget lesions involving the same organ as a single item on the CRF (for example, multiple liver metastases recorded as 1 liver lesion).

Lymph nodes with short axis  $\geq 10$  mm but < 15 mm should be considered nontarget lesions. Nodes that have a short axis < 10 mm are considered nonpathological and are not recorded or followed.

## **Specifications by Methods of Measurement**

All measurements should be recorded in metric notation, using a ruler or calipers if clinically assessed. All baseline evaluations should be performed as closely as possible to the beginning of treatment and never more than 4 weeks before the beginning of the treatment.

The same method of assessment and the same technique should be used to characterize each identified and reported lesion at baseline and during follow-up. Imaging-based evaluation is

should always be done rather than clinical examination unless the lesion(s) being followed cannot be imaged but are assessed by clinical exam.

An adequate volume of a suitable contrast agent should be given so that the metastases are demonstrated to best effect and a consistent method is used on subsequent examinations for any given patient. If prior to enrollment it is known a patient is not able to undergo CT scans with IV contrast due to allergy or renal insufficiency, the decision as to whether a non-contrast CT or MRI (with or without IV contrast) should be used to evaluate the patient at baseline and follow-up should be guided by the tumor type under investigation and the anatomic location of the disease.

*Clinical Lesions:* Clinical lesions will only be considered measurable when they are superficial and  $\geq 10$  mm diameter as assessed using calipers (for example, skin nodules). For the case of skin lesions, documentation by color photography, including a ruler to estimate the size of the lesion is recommended. When lesions can be evaluated by both clinical exam and imaging, imaging evaluation should be undertaken since it is more objective and may be reviewed at the end of the study.

*Chest X-ray*: Chest CT is preferred over chest X-ray when progression is an important endpoint. Lesions on chest X-ray may be considered measurable if they are clearly defined and surrounded by aerated lung.

*CT and MRI*: CT scan is the best currently available and reproducible method to measure lesions selected for response assessment. Measurability of lesions on CT scan is based on the assumption that CT slice thickness is  $\leq$ 5 mm. When CT scan have slice thickness >5 mm, the minimum size for a measurable lesion should be twice the slice thickness. MRI is also acceptable in certain situations (for example, for body scans). If there is concern about radiation exposure at CT, MRI may be used instead of CT in selected instances.

*Ultrasound:* Ultrasound should not be used to measure lesion size. Ultrasound examinations cannot be reproduced in their entirety for independent review at a later date and, because they are operator dependent, it cannot be guaranteed that the same technique and measurements will be taken from one assessment to the next. If new lesions are identified by ultrasound in the course of the study, confirmation by CT or MRI is advised.

*Endoscopy, Laparoscopy*: The utilization of these techniques for objective tumor evaluation is not advised. However, such techniques can be useful to confirm complete pathological response when biopsies are obtained or to determine relapse in trials where recurrence following complete response or surgical resection is an endpoint.

*Tumor Markers*: Tumor markers alone cannot be used to assess tumor response. If markers are initially above the upper normal limit, they must normalize for a patient to be considered in complete response (CR). Specific guidelines for both prostate-specific antigen (PSA) response (in recurrent prostate cancer) and CA-125 response (in recurrent ovarian cancer) have been published.

*Cytology, Histology*: These techniques can be used to differentiate between partial responses (PR) and complete response (CR) in rare cases if required by protocol (for example, residual lesions in tumor types such as germ cell tumors, where known residual benign tumors can remain). When effusions are known to be a potential adverse effect of treatment (for example, with certain taxane compounds or angiogenesis inhibitors), the cytological confirmation of the neoplastic origin of any effusion that appears or worsens during treatment can be considered if the measurable tumor has met criteria for response or SD in order to differentiate between response (or SD) and progressive disease (PD).

*Pet Scan (FDG-PET, PET CT)*: PET is not recommended for lesion assessment. If a new lesion is found by PET, another assessment must be done by CT, unless the PET CT is of diagnostic quality. If CT is done to confirm the results of the earlier PET scan, the date of progression must be reported as the earlier date of the PET scan.

*Bone Scan*: If lesions measured by bone scan are reported at baseline, it is necessary to repeat the bone scan when trying to identify a complete response (CR) or partial response (PR) in target disease or when progression in bone is suspected.

## **Response Criteria**

## **Evaluation of Target Lesions**

*Complete Response (CR):* Disappearance of all target lesions. Any pathological lymph nodes (whether target or non-target) must have reduction in short axis to <10 mm. Tumor marker results must have normalized.

*Partial Response (PR):* At least a 30% decrease in the sum of diameter of target lesions, taking as reference the baseline sum diameters.

*Progressive Disease (PD):* At least a 20% increase in the sum of the diameters of target lesions, taking as reference the smallest sum on study (including the baseline sum if that is the smallest). In addition to the relative increase of 20%, the sum must also demonstrate an absolute increase of at least 5 mm. The appearance of 1 or more new lesions is also considered progression.

For equivocal findings of progression (for example, very small and uncertain new lesions; cystic changes or necrosis in existing lesions), treatment may continue until the next scheduled assessment. If at the next scheduled assessment, progression is confirmed, the date of progression should be the earlier date when progression was suspected.

*Stable Disease (SD):* Neither sufficient shrinkage to qualify for PR nor sufficient increase to qualify for PD, taking as reference the smallest sum diameters while on study.

*Not Evaluable:* When an incomplete radiologic assessment of target lesions is performed or there is a change in the method of measurement from baseline that impacts the ability to make a reliable evaluation of response.

## **Evaluation of Nontarget Lesions**

*Complete Response:* Disappearance of all nontarget lesions and normalization of tumor marker level. All lymph nodes must be non-pathological or normal in size (<10mm short axis).

*Non-CR/ non-PD:* Persistence of 1 or more nontarget lesions and/or maintenance of tumor marker level above the normal limits.

*Progressive Disease:* Unequivocal progression of existing nontarget lesions. The appearance of 1 or more new lesions is also considered progression.

Not Evaluable: When a change in method of measurement from baseline occurs and impacts the ability to make a reliable evaluation of response.

## **Evaluation of Best Overall Response**

The best overall response (BOR) is the best response recorded from the start of the study treatment until the earliest of objective progression or start of new anticancer therapy, taking into account any requirement for confirmation. The patient's best overall response assignment will depend on the findings of both target and nontarget disease and will also take into consideration the appearance of new lesions. The BOR will be calculated via an algorithm using the assessment responses provided by the investigator over the course of the trial.

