# 9.6.1. Best Supportive Care

Palliative and supportive care for other disease-related symptoms and for toxicity associated with treatment will be offered to all patients on this trial. Supportive care measures may include but are not limited to antidiarrheal agents, antiemetic agents, opiate and nonopiate analgesic agents, appetite stimulants, and granulocyte and erythroid growth factors. Details of interventions (for example, medications such as sedatives, antibiotics, analgesics, antihistamines, steroids, or erythroid-stimulating agents), procedures (for example, paracentesis or thoracentesis), or blood products (for example, blood cells, platelets, or fresh frozen plasma transfusions) should be recorded on the electronic case report forms (eCRFs). If it is unclear whether a therapy should be regarded as supportive care, the investigator should consult the Lilly CRP. Use of any

supportive care therapy should be reported on the CRFs. Guidelines regarding the use of other specific supportive care agents are presented below.

Additional concurrent chemotherapy, radiation therapy (except as noted in Section 9.6.1.1), biologic response modifiers, or other investigational agents may not be administered to patients on this study.

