### 9.6.1.1. Palliative Radiotherapy

Palliative radiotherapy, unless required due to progressive disease, is permitted during the study.

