# 10.1.4. Secondary Efficacy Measures

Tumor response is defined by RECIST v1.1 (Eisenhauer et al. 2009) provided in Attachment 5. To derive the overall response rate, a responder is defined as any patient who exhibits a confirmed CR or PR. Best response is determined from the sequence of responses assessed.

A second assessment must be performed  $\geq 28$  days after the first evidence of response. The next scheduled scan at 56 days (8 weeks) would qualify for response confirmation. Two objective status determinations of CR before progression are required for a best response of CR. Two determinations of PR or better before progression, but not qualifying for a CR, are required for a best response of PR. Best response of SD is defined as disease that does not meet the criteria for CR, PR, or PD and has been evaluated at least 1 time, at least 6 weeks after the start of study treatment.

Best response will be derived to encompass all tumor assessments from baseline until the earliest of objective progression or start of new anticancer therapy. Any responses observed after objective progression or the start of new anticancer therapy are excluded from the determination of best response.

Progression-free survival will be defined as the time from randomization until the first evidence of objective progression as defined by RECIST v1.1 (Eisenhauer et al. 2009), or death from any cause, whichever is earlier. Patients who are not known to have either progressed or died at the time of analysis will be censored at the day of their last radiographic tumor assessment, if available, or the date of randomization if no postbaseline radiographic assessment is available. The detailed censoring rules are described in Table JPBK.12.2.

The PFS analysis will be based on the local investigator's tumor assessments.

The date of first documented objective disease progression must be recorded on the CRF even if it occurs after the patient has started a new therapy. Lilly or its designee will collect and store all tumor measurement images on all enrolled patients throughout the study. A central review of imaging scans may be performed by Lilly or its designee.

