Best overall response (BOR) will be derived to encompass all tumor assessments (according to RECIST v1.1) from baseline until the earliest of objective progression or start of new anticancer therapy. Any responses observed after objective progression or the start of new anticancer therapy are excluded from the determination of best response. Each patient's BOR will categorized as complete response (CR), partial response (PR), stable disease (SD), progressive disease (PD), or not evaluable (NE).

Overall Response Rate (ORR) is defined as the proportion of patients with BOR of CR or PR (according to RECIST v1.1). Disease control rate (DCR) is defined as the proportion of patients with BOR of CR, PR or SD (according to RECIST v1.1).

Point estimates and 95% confidence intervals (using the normal approximation to the binomial) will be calculated for ORR and DCR by treatment arm. Stratified tests comparing these rates between treatment arms will be conducted using a Cochran-Mantel-Haenszel (CMH) test adjusted by all stratification factors.

Duration of response (DoR) will be presented for responders (patients with a BOR of CR or PR according to RECIST 1.1). DoR is defined as the time from the date of the first evidence of CR or PR to the date of investigator-determined objective progression or the date of death due to any cause, whichever is earlier. DoR will be censored according to the same rules as PFS (presented in Table JPBK.6.1). The median duration of response will be summarized using K-M

techniques. The statistical comparison of DoR between treatment groups will be conducted using unstratified log-rank test and HR will be estimated using an unstratified Cox model with only the treatment factor in the model.

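### Best overall response has no rule for a target lesion irradiated on study, so shrinkage from permitted palliative radiotherapy can be scored as a partial response

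*Protocol*

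**What the plan says.** **Radiotherapy on treatment.** Protocol 9.6.1.1, a subsection of Best Supportive Care, states: "Palliative radiotherapy, unless required due to progressive disease, is permitted during the study". Section 9.6.1 bans concurrent anticancer treatment but carves this out: "radiation therapy (except as noted in Section 9.6.1.1), biologic response modifiers, or other investigational agents may not be administered". Neither section distinguishes target from non-target lesions.

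**Best overall response (BOR).** Attachment 5 takes "the best response recorded from the start of the study treatment until the earliest of objective progression or start of new anticancer therapy". Protocol 10.1.4 agrees: "Best response will be derived to encompass all tumor assessments from baseline until the earliest of objective progression or start of new anticancer therapy". SAP 6.2.10.3 reads assessments "from baseline until the earliest of objective progression or start of new anticancer therapy" and adds: "Any responses observed after objective progression or the start of new anticancer therapy are excluded from the determination of best response". ORR and DCR are proportions of BOR categories, and DoR is computed among BOR responders. Neither document defines new anticancer therapy.

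**Irradiated lesions.** The only such text in Attachment 5 opens "Tumor lesions situated at a previously irradiated area". It stands under lesion measurability, ahead of the baseline choice of target lesions.

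**PFS Sensitivity Analysis 1.** Protocol 12.2.8 names radiotherapy among the therapies that trigger censoring. The version in SAP 6.2.10.4 does not.

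**The concern.** A target lesion can be irradiated for symptoms while the patient stays on study drug and remains in the response window. If the lesion then shrinks, the plan does not say whether the later sum of diameters still measures drug response. The BOR algorithm uses investigator assessments in an open-label trial, so the people who decide on radiotherapy and on continuing drug know the arm. The arm with longer treatment also has more time in which radiotherapy can be given.

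At stake is the interpretation of secondary endpoints that are compared formally between arms: ORR, DCR and DoR, and to a lesser extent PFS. The documents would also make an imbalance hard to see. Radiotherapy use is collected (protocol 10.2.2), but the resource-utilization list in SAP 6.2.13.1 names radiotherapy only after discontinuation.

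**Working it through.** **Step 1. Is there any rule that takes the irradiated lesion out?**

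| Place | What it covers | Target lesion irradiated on study? |
|---|---|---|
| BOR in protocol 10.1.4, Attachment 5, SAP 6.2.10.3 | Stops at objective progression or new anticancer therapy | Not named |
| Attachment 5, prior local treatment | Measurability when lesions are chosen | No |
| Attachment 5, Not Evaluable (target lesions) | Incomplete assessment or changed method | No |
| PFS tables JPBK.12.1 (protocol) and JPBK.6.1 (SAP) | Seven situations | No |
| Protocol 12.2.8, PFS Sensitivity Analysis 1 | Names radiotherapy; PFS only; optional | Arguable |
| SAP 6.2.10.4, PFS Sensitivity Analysis 1 | Names systemic therapy only | No |

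Unless radiotherapy is itself read as new anticancer therapy, the lesion stays in the sum.

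**Step 2. When does this produce a PR?** The threshold is "At least a 30% decrease in the sum of diameter of target lesions", against the baseline sum. With k equal target lesions, one irradiated and shrinking by a fraction s while the rest are unchanged, the sum changes by −s/k. PR needs s ≥ 0.30k.

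| Target lesions k | Sum change at s = 60% | s needed for PR |
|---|---|---|
| 1 | −60% | 30% |
| 2 | −30% | 60% |
| 3 | −20% | 90% |
| 4 | −15% | 120%, impossible |
| 5 | −12% | 150%, impossible |

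For k = 2 at 40 mm each: (40 + 16)/80 − 1 = −30%, a PR. Attachment 5 allows up to five target lesions, so the exposure lies mainly in patients with one or two, or with one lesion that dominates the sum. The confirmation scan at 28 days or more (10.1.4) does not remove it, because radiation shrinkage can persist.

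**Step 3. When can it delay PD?** PD by the sum needs at least +20% and +5 mm over the smallest sum on study.

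- Two 40 mm lesions, one growing to 56 mm, the other irradiated to 20 mm in the same interval: 76/80 − 1 = −5%, SD. Without the shrinkage: 96/80 − 1 = +20%, +16 mm, PD.
- If the shrinkage is recorded one scan earlier, the smallest sum is 20 + 40 = 60 mm, and 76/60 − 1 = +26.7%, +16 mm. PD is called.
- Where PD is missed, the new reference is 76 mm. PD follows at 1.2 × 76 = 91.2 mm, when the growing lesion reaches 91.2 − 20 = 71.2 mm.
- With three 40 mm lesions, one growing to 56 mm gives 136/120 − 1 = +13.3%. That is SD with no radiation, so there is nothing to hide.
- New lesions and unequivocal non-target progression remain PD in every case.

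**Step 4. Scale on ORR (assumed rates; the documents give none).** ORR inflation = share with a target lesion irradiated × share crossing −30%.

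- 1% × 0.5 = 0.5 points; 5% × 0.5 = 2.5 points. In 270 patients that is 1.35 to 6.75 false responders; in 180, 0.9 to 4.5.
- If use were 5% in one arm and 1% in the other, the ORR difference would be 4 × 0.5 = 2 points with no drug effect.
- For illustration, take equal true ORR of 3 to 10% and place the false responders in the 270-patient arm only. A two-proportion normal approximation then gives a nominally significant difference in that arm's favour with probability 5.1 to 7.5% (1 extra point) or 9.3 to 16.6% (2 extra points), against a nominal 2.5%. The SAP's stratified CMH test may differ somewhat.

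**Step 5. Primary endpoint.** Events = (1.960 + 0.842)² / [0.6 × 0.4 × (ln 0.72)²] = 7.849/0.02590 = 303.05, rounded up to 304 as planned. OS uses deaths only and is untouched.

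**The case against.** The strongest reply is that new anticancer therapy is undefined and could include radiotherapy. Inclusion criterion 7 lists radiotherapy among therapies for cancer, protocol 12.2.4.1 lists it as a type of postdiscontinuation therapy, and 9.6.1 bans it alongside chemotherapy before making the exception. In 12.2.8 the list of triggering therapies is inclusive, and the word postdiscontinuation may qualify only the systemic therapy. This stands as far as it goes: the documents contain an ambiguity, not a stated rule that radiation shrinkage is drug response. But placement under supportive care, the explicit exemption, and the SAP's omission of radiotherapy point the other way. Two programmers could derive different ORRs from the same data.

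It is also fair that the PR example sits exactly on the threshold and fails with three or more equal lesions at the same shrinkage. Radiotherapy required because of progression is outside the permission, which narrows the exposed group. Declaring the whole target sum not evaluable after radiotherapy could disturb the PFS rows that depend on an adequate assessment. All of this stands, and it limits both the size of the point and the form of the remedy.

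A reader might infer that radiotherapy generally hides progression, or that it distorts the futility look at a PFS hazard ratio of 0.95. Step 3 shows that masking needs few target lesions and shrinkage and growth within the same interval. Nothing in the documents allows an effect on the PFS hazard ratio to be calculated.

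**Conclusion.** The gap holds in a bounded form. On the natural reading of the three BOR definitions, shrinkage of a target lesion irradiated on study can be scored as a PR, mainly with one or two target lesions. In limited circumstances it can also delay target-sum PD. ORR, DCR and DoR are exposed, PFS less so, and the primary OS analysis and its 304 events are unaffected.

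The 0.5 to 2.5 point ORR range rests on two assumptions: that 1 to 5% of patients have a target lesion irradiated on treatment, and that half of these cross −30%. The second looks high outside patients with one or two target lesions. It would be tempting to conclude that the comparison is biased toward abemaciclib. The documents do not support that: they give no on-study radiotherapy rate by arm, so neither size nor direction is known. The change is worth making because the missing rule is cheap to supply and the assessments are open-label.

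**What to change.** The change is to the analysis only and does not alter who may receive radiotherapy.

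1. In protocol 10.1.4, Attachment 5 and SAP 6.2.10.3, end the BOR window for CR, PR and SD at the earliest of objective progression, new anticancer therapy, or first on-study radiotherapy to a target lesion.
2. Leave the main PFS definition and its censoring rows based on adequate assessments as they are.
3. Reconcile PFS Sensitivity Analysis 1 between protocol 12.2.8 and SAP 6.2.10.4. Either that analysis or an added one should censor at the last assessment before on-study radiotherapy to a target lesion.

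Cost: a clause in each of three places and one aligned sensitivity analysis. Radiotherapy use is already collected under 10.2.2, but the irradiated site must be available from that record, which is an assumption. ORR may be slightly lower, partly because a true response whose confirming scan falls after radiotherapy would no longer count as confirmed. The sensitivity censoring may be informative, since symptoms that prompt radiotherapy can precede progression, so it should support the main PFS result and not replace it.
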